5.4. Cohort 3 (Post-Chemo Maint Mag+CC-486)

The start of the cycle is the first day of CC-486.

Information for magnolimab is provided in Section 5.1. CC-486 is to be administered before magnolimab in Cycle 1.

5.4.1. Description and Handling of CC-486

5.4.1.1. Formulation

Information regarding the formulation of CC-486 can be found in the current prescribing information {ONUREG 2020}.

5.4.1.2. Packaging and Labeling

Study drug(s) to be distributed to centers in the US and other participating countries shall be labeled to meet applicable requirements of the US FDA, EU Guidelines to Good Manufacturing Practice, Annex 13 (Investigational Medicinal Products), and/or other local regulations.

5.4.1.3. Storage and Handling

Further information regarding storage and handling of CC-486 is available in the local prescribing information {ONUREG 2020}.

5.4.2. Dosing and Administration of CC-486

The CC-486 dosing regimen for Safety Run-in Cohort 3 is presented in Table 3. The dose de-escalation regimens for CC-486 in Safety Run-in Cohort 3 are presented in Table 6. The treatment schedule is provided in Appendix Table 8.

If a patient discontinues CC-486, magrolimab should also be discontinued.

CC-486 (Onureg) will be administered at a dose of 300 mg orally once daily on Days 1 through 14 of each 28-day cycle in accordance with USPI. CC-486 should be taken at the same time each day. If a dose of CC-486 is missed, or not taken at the usual time, the dose should be taken as soon as possible on the same day, and the normal dosing schedule resumed the following day. Two doses should not be taken on the same day. CC-486 should not be substituted with IV or SC azacitidine products. CC-486 treatment will be administered until disease progression, unacceptable toxicity, and/or loss of clinical benefit.

5.4.3. Premedication and Prophylaxis for CC-486

An anti-emetic should be administered 30 minutes prior to each dose of CC-486 for the first 2 cycles. Anti-emetic prophylaxis may be omitted after 2 cycles if there has been no nausea or vomiting. Anti-emetic regimens can be administered by USPI or local institutional guidelines.

5.4.4. Dose Modification and Delays for CC-486

CC-486 can cause myelosuppression, gastrointestinal toxicity, and other toxicities. Dose modifications/reductions of CC-486 will be made in accordance with the US package insert. Dose modifications for these toxicities are described in Table 12.

Table 12. CC-486 Dose Modifications for Adverse Reactions

Adverse Reaction	Severity	Dose Modification ^a
Myelosuppression	Neutrophils less than 0.5 Gi/L on Day 1 of the cycle	Interrupt treatment. Resume at the same dose once neutrophils return to 0.5 Gi/L or higher.
	Neutrophils less than 1 Gi/L	First occurrence:
	with fever at any time	Interrupt treatment. Resume at the same dose once neutrophils return to 1 Gi/L or higher.
		Occurrence in 2 consecutive cycles:
		Interrupt treatment. After neutrophils return to 1 Gi/L or higher, resume at reduce dose of 200 mg.
		If a patient continues to experience febrile neutropenia after dose reduction, reduce the treatment duration by 7 days.
		If febrile neutropenia reoccurs after dose and schedule reduction, discontinue CC-486.
	Platelets less than 50 Gi/L with bleeding	First occurrence: Interrupt treatment. Resume at the same dose once platelets return to 50 Gi/L or higher.
		Occurrence in 2 consecutive cycles:
		Interrupt treatment. After platelets return to 50 Gi/L or higher, resume at reduced dose of 200 mg.
		If a patient continues to experience thrombocytopenia with bleeding after dose reduction, reduce the treatment duration by 7 days.
		If thrombocytopenia with bleeding reoccurs after dose and schedule reduction, discontinue CC-486.
Gastrointestinal toxicity	Grade 3 or 4 nausea or vomiting	Interrupt dosing, resume at the same dose once toxicity has resolved to Grade 1 or lower (or baseline).
		If toxicity recurs, interrupt dosing until resolved to Grade 1 or lower (or baseline). Resume at reduced dose of 200 mg.
		If a patient continues to experience the toxicity after dose reduction, reduce the treatment duration by 7 days.
		If the toxicity continues or recurs after dose and schedule reduction, discontinue CC-486.
	Grade 3 or 4 diarrhea	Interrupt dosing, resume at the same dose once toxicity has resolved to Grade 1 or lower (or baseline).
		If toxicity recurs, interrupt dosing until resolved to Grade 1 or lower (or baseline). Resume at reduced dose of 200 mg.
		If a patient continues to experience the toxicity after dose reduction, reduce the treatment duration by 7 days.
		If the toxicity continues or recurs after dose and schedule reduction, discontinue CC-486.

Adverse Reaction	Severity	Dose Modification ^a
Other Adverse Reactions	Grade 3 or 4	Interrupt dosing, resume at the same dose once toxicity has resolved to Grade 1 or lower (or baseline).
		If toxicity recurs, interrupt dosing until resolved to Grade 1 or lower (or baseline). Resume at reduced dose of 200 mg.
		If a patient continues to experience the toxicity after dose reduction, reduce the treatment duration by 7 days.
		If the toxicity continues or recurs after dose and schedule reduction, discontinue CC-486.

Gi = giga per liter; PO = per oral route; RP2D = recommended Phase 2 dose

5.4.5. Prior and Concomitant Medications: Prohibited Concomitant Medications for Cohort 3

For the anti-leukemia regimens administered with magnolimab in this study, the current local or regional prescribing information should be consulted regarding permitted and prohibited concomitant medications.

Anti-leukemic therapies, including chemotherapy (with the exception of hydroxyurea), targeted therapies, and immunotherapy, are not permitted while patients are on study treatment.

Any investigational drugs other than those used in the study are prohibited during study treatment.

5.5. Accountability for Investigational Medicinal Product

The investigator is responsible for ensuring adequate accountability of all used and unused study drug (kits, vials, etc.) This includes acknowledgment of receipt of each shipment of study drug (quantity and condition). All used and unused study drug dispensed to patients must be returned to the site.

Each study site must keep accountability records that capture the following:

- The date received and quantity of study drug (kits, vials, etc.).
- The date, patient number, and the study lot number dispensed.
- The date, quantity of used, and unused study drug returned, along with the initials of the person recording the information.

a If a 200 mg PO dose of CC-486 is selected as the RP2D, then omit further dose reduction and go directly to language "reduce the treatment duration by 7 days".

5.5.1. Investigational Medicinal Product Return or Disposal

Gilead recommends that used and unused study drug supplies be destroyed at the site. If the site has an appropriate standard operating procedure (SOP) for drug destruction as determined by Gilead, the site may destroy used (empty or partially empty) and unused study drug supplies in accordance with that site's approved SOP. A copy of the site's approved SOP will be obtained for the electronic trial master file. If study drug is destroyed at the site, the investigator must maintain accurate records for all study drugs destroyed. Records must show the identification and quantity of each unit destroyed, the method of destruction, and the person who disposed of the study drug. Upon study completion, copies of the study drug accountability records must be filed at the site. Another copy will be returned to Gilead.

If the site does not have an appropriate SOP for drug destruction, used and unused study drug supplies are to be sent to the designated disposal facility for destruction. The study monitor will provide instructions for return.

The study monitor will review study drug supplies and associated records at periodic intervals.

6. STUDY PROCEDURES

The study procedures to be conducted for each patient enrolled in the study are presented in tabular form in Appendix 2 (Appendix Table 1, Appendix Table 2, Appendix Table 3, Appendix Table 4, Appendix Table 5, and Appendix Table 9) and described in the text that follows.

The investigator must document any deviation from the protocol procedures and notify Gilead or the contract research organization.

Refer to Section 3.1.3 for information on Cohort 1 patients enrolled prior to implementation of Protocol Amendment 5

6.1. Patient Enrollment and Treatment Assignment

Entry into screening does not guarantee enrollment into the study. In order to manage the total study enrollment, Gilead, at its sole discretion, may suspend screening and/or enrollment at any site or study wide at any time.

Patients who meet eligibility criteria will be enrolled using an integrated web response system. The first dose of study drugs should be administered within 72 hours after enrollment.

Patients who are determined to be not eligible after screening may be rescreened once at the discretion of the investigator. Rescreening must be discussed with and approved by the study medical monitor on a case-by-case basis. Patients who are determined to be eligible for rescreening must be reconsented with a new screening number assigned.

6.2. Pretreatment Assessments

6.2.1. Screening Visit

Screening assessments are outlined in Appendix Table 1.

Patients will be screened within 30 days before enrollment to determine eligibility for participation in the study. The following will be performed and documented at screening:

- Obtain written informed consent
- Obtain demographics and medical history, including cancer history, date of recent RBC and/or platelet transfusions, AML molecular marker results at diagnosis, and echocardiogram/multigated acquisition (scan) (MUGA) or pulmonary function tests if done within the 3 months prior to signing the informed consent form (ICF)
- Complete physical examination, including vital signs, body weight, and height
- Serum pregnancy test (females of childbearing potential)

- Complete blood count (CBC) with differential, platelets, reticulocytes
- Serum or plasma chemistry
- Prothrombin time, INR, and activated partial thromboplastin time or partial thromboplastin time
- Extended red blood cell phenotyping or genotyping, ABO system (ABO)/Rhesus factor (Rh) type, and screen (any of the 4 blood groups A, B, AB, and O composing the ABO/Rh), direct antiglobulin test (DAT)
- Urinalysis
- Bone marrow biopsy and aspirate for blast evaluation, MRD assessment, cytogenetics, and correlative studies
- Bone marrow aspirate for RO (to be collected at selected study sites)
- Peripheral blood smear (for blasts)
- ECOG performance status (Appendix 6)
- Perform 12-lead electrocardiogram (ECG) (single)
- Echocardiogram or MUGA, if not done within the past 30 days prior to consent, for Cohort 2 patients only
- Record all SAEs and any AEs related to protocol-mandated procedures occurring after signing of the ICF
- Record prior and concomitant medications
- Entry criteria

From the time of obtaining informed consent through the first administration of study drug, record all SAEs, as well as any AEs related to protocol-mandated procedures on the AEs eCRF. All other untoward medical occurrences observed during the screening period, including exacerbation or changes in medical history, are to be considered medical history. Additional details are provided in Section 7, Adverse Events and Toxicity Management.

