17) Patients with confirmation of AML by WHO criteria who are refractory to or have experienced first relapse after initial intensive chemotherapy, which includes 1 or 2 cycles of a 7 + 3 based induction regimen or a purine analogue based induction therapy, such as fludarabine or cladribine paired with anthracyclines and cytarabine (eg, fludarabine, high-dose cytarabine [ara-C], G-CSF, and idarubicin [FLAG-Ida] or cladribine, ara-C, G-CSF, and mitoxantrone [CLAG-M]) or failed therapy after remission (eg, consolidation) during any number of cycles (maximum of 4) of high- or intermediate-dose cytarabine. For other intensive regimens, please discuss with the medical monitor.

NOTE: Patients who are relapsed after or are refractory to more than 1 line of anti-AML treatment are not eligible.

Patients who relapsed after undergoing stem cell transplant may be eligible.

18) At least 2 weeks must have elapsed since any prior anti-leukemia agents.

NOTE: Localized non-central nervous system (CNS) radiotherapy, hydroxyurea, and erythroid and/or myeloid growth factors are not criteria for exclusion.

- 19) ECOG performance status of 0 to 2.
- 20) Patients with LVEF ≥ 50%, lack of symptomatic congestive heart failure, or clinically significant cardiac arrhythmias.
- 21) Patients who have not been treated with trastuzumab within 7 months prior to the initiation of study treatment
- 22) Patients who have not previously received maximum cumulative doses of anthracyclines and anthracenediones
- 23) Patients without degenerative or toxic encephalopathies
- 24) Patients who did not undergo hematopoietic SCT in the past 100 days, are not on immunosuppressive therapy post SCT in the 2 weeks prior to the first dose of study treatment, or have no active clinically significant graft-versus-host disease.

Safety Run-in Cohort 3 and Phase 2 Cohort 3 (Post-chemo Maint Mag+CC-486), closed to enrollment globally as of Protocol Amendment 5

In addition to meeting the inclusion criteria for all patients, patients who are enrolled into Safety Run-in Cohort 3 and Phase 2 Cohort 3 must fulfill the following cohort-specific inclusion criteria:

- 25) Patients with confirmation of AML by WHO criteria who achieved a CR or CRi with presence of MRD (MRD positive by local flow cytometry assay, defined as ≥ 0.1% detectable MRD) after intensive induction chemotherapy with or without consolidation therapy, prior to starting maintenance therapy for newly diagnosed AML.

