7.8.4. Mitoxantrone

Safety management guidelines for mitoxantrone are in accordance with the prescribing information {MitoXANTRONE 2018}. Key considerations are described here.

Myelosuppression

Mitoxantrone can cause severe myelosuppression when used for AML treatment. Close monitoring of laboratory counts, infectious prophylaxis, and supportive blood products and growth factors is needed. Mitoxantrone should only be administered by physicians experienced with treating AML.

Cardiac Risk

Mitoxantrone can cause congestive heart failure during or after therapy. Cardiotoxicity risk increases with cumulative mitoxantrone use. History of cardiovascular disease, prior therapy with anthracyclines or anthracenediones or use of other cardiotoxic drugs can increase this risk. All patients should be assessed for cardiac signs and symptoms by history, physical examination, and ECG prior to the start of therapy. In addition, all patients should have an echocardiogram to evaluate LVEF prior to starting therapy.

Secondary AML

Secondary AML has been reported in patients treated with mitoxantrone. In 1774 patients with breast cancer who received mitoxantrone concomitantly with other cytotoxic agents and radiotherapy, the cumulative risk of developing treatment-related AML was estimated at 1.1% at 5 years after receiving the therapy.

Hypersensitivity Reactions

Hypersensitivity reactions to mitoxantrone, including anaphylaxis, can occur. If hypersensitivity reactions occur, immediately interrupt treatment with mitoxantrone and institute supportive management per local guidelines. Permanently discontinue mitoxantrone treatment in any patient who experiences a severe hypersensitivity reaction.

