Appendix 1. Investigator Signature Page

GILEAD SCIENCES, INC. [name]

STUDY ACKNOWLEDGMENT

A PHASE 2 MULTI-ARM STUDY OF MAGROLIMAB COMBINATIONS IN PATIENTS WITH MYELOID MALIGNANCIES

GS-US-546-5920 Protocol Amendment 6, 02 November 2023

This protocol has been approved by Gilead Sciences, Inc. The following signature documents this approval.

PPD

[See appended electronic signature]

PPD	[See appended electronic signature]
Name (Printed) Medical Monitor	Signature
[See appended electronic signature]	
Date	
INVESTIGA	ATOR STATEMENT
	ndices, and I agree that it contains all necessary study as described. I will conduct this study as effort to complete the study within the time
	supervision copies of the protocol and access to all nc. I will discuss this material with them to ensure and the study.
Principal Investigator Name (Printed)	Signature
Date	Site Number

Appendix 2. Schedules of Assessment and Treatment Administration Appendix Table 1. Schedule of Assessments – Screening

Assessment	Study Day -30 to -1
Informed consent	Xa
Demographics	X
Medical and cancer history, including date of recent RBC and/or platelet transfusions, AML molecular marker results at diagnosis (if available), and echocardiogram/MUGA or pulmonary function tests if done within the 3 months prior	X
Complete physical examination	X
Vital signs, height, and weight	X
Serum pregnancy test ^b	X
CBC with differential, platelets, reticulocytes	X
Serum or plasma chemistry	X
PT, INR, and aPTT (or PTT)	X
Extended RBC phenotyping or genotyping, type, and screen (ABO/Rh), DAT	X
Urinalysis	X
Bone marrow biopsy and aspirate for blast evaluation, MRD assessment, cytogenetics, and correlative studies ^c	X
Peripheral blood smear (for blasts) ^d	X
Bone marrow aspirate for receptor occupancy (to be collected at selected study sites) ^c	X
ECOG performance status	X
12-Lead ECG (single)	X
Echocardiogram or MUGA for Cohort 2 only (if not done in the past 30 days)	X
All SAEs and any AEs related to protocol-mandated procedures	X
Prior and concomitant medications	X
Entry criteria	X

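### Cohort 2's echocardiogram waiver looks only at scan age, so in a small subset of refractory patients the qualifying LVEF can predate the failed anthracycline induction

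*Protocol*

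**What the plan says.** Protocol Section 6.2.1 (Screening Visit) requires "Echocardiogram or MUGA, if not done within the past 30 days prior to consent, for Cohort 2 patients only". The screening schedule in Appendix Table 1 has the same waiver: "Echocardiogram or MUGA for Cohort 2 only (if not done in the past 30 days". Neither place adds a condition about treatment given between the scan and consent.

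The Cohort 2 criteria in Section 4.2 set the other limits:

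- Criterion 20: "Patients with LVEF ≥ 50%, lack of symptomatic congestive heart failure, or clinically significant cardiac arrhythmias". The LVEF carries no date.
- Criterion 17 admits patients refractory to, or in first relapse after, initial intensive chemotherapy, "which includes 1 or 2 cycles of a 7 + 3 based induction regimen" or a purine analogue regimen with an anthracycline. One of its examples, CLAG-M, contains mitoxantrone.
- Criterion 18: "At least 2 weeks must have elapsed since any prior anti-leukemia agents".

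On cardiac risk, Section 7.8.4 says "prior therapy with anthracyclines or anthracenediones or use of other cardiotoxic drugs can increase this risk", and adds: "In addition, all patients should have an echocardiogram to evaluate LVEF prior to starting therapy".

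**The concern.** The scan is there to show that cardiac function is adequate before mitoxantrone is given to patients who have nearly all had an anthracycline or anthracenedione already. A scan taken before the failed induction cannot show the effect of that induction, yet the waiver accepts it as long as it is no more than 30 days old at consent.

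Mitoxantrone starts on Cycle 1 Day 1 and is given for 2 to 3 cycles. The Cohort 2 on-treatment schedule (Appendix Table 3) and the post-treatment schedule (Appendix Table 9) contain no echocardiogram or MUGA. If the screening scan is waived, the schedule yields no LVEF after the failed induction. At stake is the cardiac safety of the affected patients. The power calculation and the primary analysis are not touched.

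**Working it through.** The plan gives no figure on this point to reproduce. The question is whether its time windows allow the sequence scan, failed induction, consent, first dose.

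**Inputs from the protocol**

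- Waiver: scan no more than 30 days before consent (Section 6.2.1).
- Washout: 14 days (criterion 18).
- Consent to enrollment: up to 30 days. Enrollment to first dose: up to 72 hours (Appendix Table 1, footnote a).

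**Assumptions, not in the documents**

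- The scan is *g* = 1, 3 or 7 days before induction Day 1.
- 7+3 lasts 7 days; a range of 5 to 10 days is used for induction length *L* in check 2.
- The refractory marrow is on induction day *m* = 14, 21 or 28.

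**Check 1: days left to consent after the marrow.** The marrow is (*m* − 1) + *g* days after the scan, so days left = 30 − *g* − (*m* − 1).

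| Scan before Day 1 | Marrow Day 14 | Marrow Day 21 | Marrow Day 28 | Latest consent (Day 31 − *g*) |
|---|---|---|---|---|
| 1 day | 16 | 9 | 2 | Day 30 |
| 3 days | 14 | 7 | 0 | Day 28 |
| 7 days | 10 | 3 | none (−4) | Day 24 |

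**Check 2: a stricter version, with consent held until the washout is complete.** Counting from the scan, the last induction day is *g* + *L* − 1 and the washout ends at *g* + *L* − 1 + 14.

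- *g* = 1, *L* = 7: the washout ends on day 21, leaving 30 − 21 = 9 days.
- *g* = 7, *L* = 7: day 27, leaving 3 days.
- Extremes: *g* = 1, *L* = 5 gives day 19 (11 days left); *g* = 7, *L* = 10 gives day 30 (0 days left).

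Every single-cycle case in this range fits.

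**Worked example.** The scan is 3 days before 7+3 Day 1, the refractory marrow is on Day 21 and consent is on Day 22.

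- Scan age at consent: 22 − 1 + 3 = 24 days, which is 30 − 24 = 6 days inside the limit. No new scan is required.
- First dose on induction Day 28: 28 − 7 = 21 days after the last 7+3 day, so the 14-day washout is met (earliest possible first dose is Day 7 + 14 = Day 21).

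**Two induction cycles.** If the second cycle starts 21 to 28 days after the first, the washout ends 19 + 21 = 40 to 30 + 28 = 58 days after a scan taken before cycle 1. Consent after the washout is then too late for the waiver, so most such scans drop out. Relapsed patients mostly drop out too, because their induction lies well before the 30-day window.

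**Upper bound on scan age.** The oldest scan that can stand at first dose is 30 + 30 + 3 = 63 days.

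**The case against.** The strongest reply is that the waiver lines only schedule a procedure, while eligibility rests on criterion 20, which is written in the present tense. An investigator who knows that an anthracycline followed the scan must still judge whether the LVEF is adequate now. Section 7.8.4, read in context, wants a cardiac baseline before mitoxantrone in patients with prior exposure.

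The needed facts are also collected. The history must record an echocardiogram or MUGA "or pulmonary function tests if done within the 3 months prior to signing the informed consent form (ICF", and prior medications, a full examination and an ECG are required. Criterion 22 excludes patients at the maximum cumulative anthracycline dose, exclusion 10 covers significant cardiac disease, and mitoxantrone may be given only by physicians experienced with AML. Section 7.8.4 also defers to the mitoxantrone prescribing information, which may ask for more. Finally, the case needs a particular sequence of dates in a cohort of about 36, and no frequency is given.

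Much of this stands as mitigation: the order of scan and induction is visible in the record, and a careful investigator would often repeat the scan. It does not close the gap. Section 7.8.4 asks for a scan before therapy, and a pre-induction scan is before therapy. Criterion 22 counts dose rather than function, and exclusion 10 would not catch an asymptomatic fall in LVEF. None of these provisions requires a repeat scan, and the two places that govern the procedure say it may be skipped. The prescribing information is not available here, so the conclusion is limited to the protocol text.

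**Conclusion.** The concern holds. The protocol waives its only scheduled Cohort 2 LVEF measurement on scan age alone, and its own windows allow that scan to predate the failed anthracycline induction.

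The affected group is small: mainly primary refractory patients after one cycle, scanned shortly before induction, with a marrow around Day 14 to 21 and prompt consent. A Day 28 marrow leaves at most 2 days. That description rests on the assumed scan, induction and marrow timings. The documents say nothing about how often LVEF falls below 50% in this setting, so the harm is unsized. The change is worth making because the protocol itself names the risk and the remedy is cheap.

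**What to change.** In Section 6.2.1 and Appendix Table 1, add one clause to the waiver: an earlier echocardiogram or MUGA is not accepted if any anthracycline or anthracenedione was given after it. The screening scan is then done as scheduled.

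As an optional alignment, name consent as the reference date in Appendix Table 1, as Section 6.2.1 already does.

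The cost is a few more screening scans performed rather than waived. No new procedure is added.
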